3.2.2 Summary of Clinical Experience with EBR/GZR

3.2.2.1 Summary of Clinical Experience with EBR/GZR in Adults

EBR/GZR (50 mg/100 mg) ± RBV has demonstrated a favorable safety and efficacy profile in a diverse adult (≥ 18 years of age) population that included patients with compensated cirrhosis, chronic kidney disease, and HIV-1/HCV co-infection [Ferrante, S., et al 2015] [Lawitz, E., et al 2014] [Sulkowski, M., et al 2014] [Zeuzem, S., et al 2015] [Rockstroh, J. K., et al 2015] [Forns, X., et al 2015] [Buti, M., et al 2016] [Roth, D., et al 2015].

The data below provides an overview of the primary efficacy endpoint, sustained virologic response 12 weeks after the end of all study therapy (SVR₁₂), supporting final adult dosing and administration guidance.

- High response rates in GT1 and GT4 treatment-naïve (TN) subjects (SVR₁₂ of 94-96%) treated with a 12-week, RBV free regimen.
- High response rates in GT1, and GT4 PR-treatment-experienced (TE) relapsers (SVR₁₂ of 100%) treated with a 12-week, RBV free regimen.
- High response rates in GT1b PR-TE subjects who failed prior PR therapy due to either null or partial response (SVR₁₂ 100%) when treated with a 12-week, RBV free regimen.
- High response rates in all GT1 and GT4 subjects treated for 16 weeks with a regimen of EBR/GZR with RBV.
- Response rates that are comparable in Childs-Pugh A cirrhotics and noncirrhotics.

In addition to the data above, a secondary analysis has been performed that demonstrates that incorporation of resistance testing for GT1a-infected participants can be used to optimize efficacy outcomes in the minority of GT1a-infected patients with baseline NS5A resistance-associated substitutions (RASs) who may have suboptimal efficacy with a 12-week EBR/GZR regimen. These data are shown below in [Table 1](#) shows the integrated data and observed efficacy from the adult Phase II/III EBR/GZR development program when RAS

testing is incorporated into dosing and administration guidance for the GT1a population. The populations included in these integrated data include TN and TE patients with compensated cirrhosis, advanced chronic kidney disease, and both mono HCV infected and HIV-1/HCV co-infected patients.

Table 1 SVR₁₂ of EBR/GZR (50 mg/100 mg) – MK-5172 Protocols 035, 048, 052, 060, 061, and 068

Regimen	SVR ₁₂ OVERALL			
	Study Population	N	n	%
12 wks no RBV	1a TN or PR-TE Without BL RASs 28, 30, 31, 93 [†]	450	441	98.0%
	1b TN or PR-TE	301	297	98.7%
	4 TN	55	54	98.2%
16 wks + RBV	1a TN or PR-TE With BL RASs 28, 30, 31, 93 [†]	6	6	100%
	4 PR-TE	8	8	100%
Based on the modified Full Analysis Set population that excludes subjects who discontinued from the study for non-treatment-related reasons.				
[†] In GT1a subjects, subjects without baseline NS5A sequencing information are excluded.				
N: Number of subjects in population.				
n: Number of subjects who achieved SVR ₁₂ .				
BL = baseline; GT = genotype; PR = pegylated-interferon with RBV; RAS = resistance-associated substitution; RBV = ribavirin; SVR ₁₂ = sustained virologic response 12 weeks after the end of all study therapy; TE = treatment-experienced; TN = treatment-naïve.				

Recommendations for dosing and administration of EBR/GZR have incorporated viral load, GT, treatment history, and GT/subtype and presence of baseline NS5A RASs. The recommendations adopted vary by region (eg, US vs European Union [EU]), in part due to the regional variability in availability of commercial RAS testing. In the US, the addition of RBV and lengthening the treatment duration to 16 weeks are recommended for the small subset of GT1a-infected patients with baseline RASs. In the EU, the addition of RBV and lengthening the treatment duration to 16 weeks are recommended for GT1a-infected patients with high viral load at baseline.

In this trial, in order to provide a simple regimen of 12 weeks without RBV (and applicable to both the EU and US prescribing information), only participants with HCV GT1 or with GT4 and HCV ribonucleic acid (RNA) <800,000 IU/mL will be enrolled. In addition, for those with GT1a infection, RAS testing will be used and only those without a baseline NS5A RAS at position 28, 30, 31, and/or 93 will be enrolled.

3.2.3 PK Background and Strategy

In the Phase II/III EBR/GZR development program, population PK, PK/pharmacodynamics (PD), and physiologically based pharmacokinetic (PBPK) modeling supported the proper dosing for a safe and efficacious adult regimen. The PK/PD modeling for safety and efficacy were used to define the clinical comparability bounds, based on an area under the time-concentration curve (AUC) of [0.4, 5.0] for GZR and [0.5, 2.0] for EBR. Application of these models and clinical bounds will be applied to this pediatric trial to support dosing of children aged 3 years up to 18 years.

3.2.3.1 EBR/GZR Metabolism

EBR elimination in humans is via a combination of excretion of parent compound as well as oxidative metabolism (mediated via cytochrome P4503A [CYP3A]) into feces, with minimal elimination into urine. EBR is a substrate of CYP3A and P-glycoprotein (P-gp) (minor contribution). EBR exhibits linear and dose-proportional PK across the 10-100 mg dose range. HCV patients and healthy participants receiving 50-100 mg QD have comparable plasma exposures at steady-state. Following administration of EBR 50 mg QD to HCV patients, the geometric mean (GM) apparent terminal half-life is ~24 hours and steady-state is achieved within 5 days. EBR exhibits moderate bioavailability (32%), with a time to maximum concentration (T_{max}) of ~3 hours.

GZR is eliminated via biliary excretion in the form of oxidative metabolism (mediated via CYP3A4) and as GZR (likely via biliary efflux transport) in humans. GZR is a substrate of CYP3A4, P-gp (minor contribution), and the liver uptake transporters organic anion-transporting polypeptide (OATP) 1B1/3. GZR has non-linear and greater than dose-proportional plasma PK in humans, likely attributed to saturation of CYP3A metabolism and OATP1B uptake at higher doses/exposures. Steady-state GZR plasma PK is ~2-fold greater in HCV patients than in healthy participants. Following administration of GZR 100 mg QD to HCV patients, the GM apparent terminal half-life is ~31 hours. In HCV patients, the HCV viral load decline associated with the first few weeks of administration of EBR/GZR results in decreased GZR exposure (likely due to improved liver function); therefore, steady-state in patients is achieved by about TW4. GZR exhibits moderate bioavailability (10-40%), with a T_{max} of ~2 hours.

3.2.3.2 Modeling and Simulation in Adults

Population PK, PK/PD, and PBPK models have been developed for EBR and GZR in support of the adult filings.

GZR is associated with exposure-dependent alanine aminotransferase (ALT) or aspartate aminotransferase (AST) elevations that typically occur around TW 8-10. The efficacy endpoint for EBR and GZR of SVR₁₂ is also exposure-dependent. Logistic regression PK/PD models for safety and efficacy have been established using adult data. During PK/PD model development, AUC was found to be the most predictive PK parameter for both safety and efficacy. Using the PK/PD models, the therapeutic bounds, based on AUC, were defined for EBR [0.5, 2.0] and GZR [0.4, 5.0].

Based on the EBR and GZR population PK models (N=3214 total patients and healthy participants), the impact of various intrinsic factors on the plasma PK of EBR and GZR were determined and are demonstrated in the forest plot in [Figure 1](#). Several intrinsic factors affected EBR and/or GZR PK, but most changes were within the clinical comparability bounds, and therefore not clinically relevant. For example, low body weight (~37-66 kg) had an ~20% increase in AUC for both EBR and GZR, but the increase was well within the therapeutic window for both compounds. EBR/GZR are contraindicated in patients with Child-Pugh B and C cirrhosis.

PBPK models for EBR and GZR were previously developed, which incorporated the key absorption, distribution, metabolism, and excretion (ADME) and PK properties for both compounds (eg, OATP1B saturation for GZR) [M&S Analysis Rpt 2015][M&S Analysis Rpt 2015]. This modeling provided supportive mechanistic evidence and interpretation for the effect of intrinsic factors (eg, HCV infection, cirrhosis, Asian ethnicity) on the PK of EBR and GZR.

These data and models supported the approval of EBR/GZR in adults infected with HCV GT1 and/or 4 and will be updated and used to select appropriate doses for the pediatric population.

[figure not shown]

Figure 1 Impact of Intrinsic Factors on the AUC of EBR and GZR

The shaded area of [Figure 1](#) represents the region of no clinically relevant effect.

3.2.4 Preclinical Trials Supporting a Pediatric Clinical Study

Prior to initiation of the pediatric clinical trial, pre- and postnatal developmental EBR and GZR monotherapy studies have been conducted and have not identified findings of concern in rats, rabbits, and dogs. In rats, dosing did not result in any effects on development, growth, behavior, reproductive performance, or fertility following oral administration to female rats from Gestation Day 6 through Lactation Day 20. In these studies, the highest maternal GZR exposure, area under the time-concentration curve over 24 hours (AUC_{0-24}) = 155 $\mu\text{M}\cdot\text{hr}$ represents approximately 31-fold the GZR clinical target AUC_{0-24} of 5 $\mu\text{M}\cdot\text{hr}$ in humans, and the highest maternal EBR exposure, AUC_{0-24} = 21.8 $\mu\text{M}\cdot\text{hr}$ (measured in pregnant females in the embryofetal developmental and toxicokinetic [TK] study in rats) represents approximately 16-fold the EBR clinical target AUC_{0-24} of 1.35 $\mu\text{M}\cdot\text{hr}$ in humans. Additionally, EBR and GZR placental and lactational transfer studies in rats and EBR and GZR placental transfer studies in rabbits showed distribution of EBR or GZR into rat and rabbit fetal plasma and rat milk. TK parameters obtained at different animal ages in the repeat-dose EBR and GZR monotherapy studies in rats and dogs did not indicate age-related differences in plasma systemic exposures. In rats, the first TK evaluation was performed in 7-week old animals (which corresponds to an approximate human age of 12 years), and the last TK evaluation was performed in 18-week old animals (adult animals). In dogs, the first TK evaluation was performed in 26- (EBR) or 32-week old (GZR) animals (which corresponds to an approximate human age of 15-17 years), and the last TK evaluation was performed in 56- (EBR) or 78-week old (GZR) animals (adult animals).

In conclusion, pre-clinical animal studies support the use of EBR and GZR in children.

3.3 Benefit/Risk Assessment

It cannot be guaranteed that participants in clinical trials will directly benefit from treatment during participation, as clinical trials are designed to provide information about the safety and effectiveness of an investigational medicine.

Elbasvir/Grazoprevir

In Phase I-III studies, 1,234 healthy volunteers, 66 non-HCV-infected persons with liver or kidney impairment, and 2,704 HCV-infected participants have been treated with any dose or regimen of EBR and/or GZR, with or without RBV. At a dose of EBR (50 mg) and GZR (100 mg), high efficacy and a favorable safety profile have been demonstrated in approximately 2,000 participants, including participants with cirrhosis, HIV-1/HCV-coinfection, chronic kidney disease, and history of prior HCV treatment failure.

ALT elevation is a safety signal associated with increased GZR exposures. Because of this, a plan has been developed to monitor for the signal. This protocol includes predefined monitoring of Events of Clinical Interest (ECI) (Section 9.3.7), specification of ALT levels that would require discontinuation of study treatment (Section 8.1), and predefined criteria for late ALT elevations and hepatic ECI which will result in a pause in enrollment (Section 5.4.2.3.2).

Additional details regarding specific benefits and risks for participants participating in this clinical trial may be found in the accompanying IB and Informed Consent documents.

4. Objectives/Hypotheses and Endpoints

In pediatric participants (aged 3 to <18 years) with chronic hepatitis C GT1 or GT4 infection with or without compensated cirrhosis.

- GT1-infected participants who are TN or TE.
- GT4-infected participants who are TN and have HCV RNA <800,000 IU/mL.

Objective/Hypothesis	Endpoint
There are no hypotheses to be tested in this trial.	
Primary	

• Objective: To evaluate the steady-state EBR and GZR PK in children and adolescents grouped by age.	
• Week 4 AUC₀₋₂₄, maximum observed drug concentration (C_{max}), drug concentration immediately pre-dose (C_{trough}), and apparent clearance (CL/F).
Secondary	

• Objective: To evaluate the safety and tolerability of 12 weeks of treatment with EBR/GZR in children and adolescents grouped by age.	
• Number of participants experiencing AEs.• Number of participants discontinuing study drug due to AEs.

• Objective: To evaluate the efficacy of 12 weeks of treatment with EBR/GZR in children and adolescents grouped by age, as assessed by the proportion of participants achieving SVR₁₂.	
• SVR₁₂: defined as HCV RNA <lower limit of quantification (LLOQ) (either target detected, but unquantifiable [TD(u)] or target not detected [TND]) 12 weeks after the end of all study therapy.
Exploratory	

• Objective: To evaluate the efficacy of 12 weeks of treatment with EBR/GZR in children and adolescents grouped by age, as assessed by the proportion of participants achieving sustained virologic response 24 weeks after the end of all study therapy (SVR₂₄).	
• SVR₂₄: defined as HCV RNA <LLOQ (either TD[u] or TND) 24 weeks after the end of all study therapy.

Objective/Hypothesis	Endpoint

• Objective: To evaluate the emergence of NS3 and NS5A RASs in participants with virologic failure.	
• Treatment-emergent RASs to EBR/GZR.

• Objective: To evaluate the palatability and acceptability of treatment with EBR/GZR.	
• Score on a palatability scale.

• Objective: To evaluate growth in children treated with EBR/GZR.	
• Changes from baseline for height and weight by age.

5. Study Design

5.1 Overall Design

This is a non-randomized, single arm, multiple cohort, multi-site, open-label Phase IIb trial of EBR/GZR in pediatric participants aged 3 to less than 18 years with chronic HCV infection GT1b/1-other; GT1a without baseline NS5A RAS at positions 28, 30, 31, and/or 93; or GT4, to be conducted in conformance with Good Clinical Practice.

The goals of this Phase IIb trial are: 1) to define doses for EBR/GZR in children by assessing plasma PK concentrations that target a similar PK to that seen in adults receiving EBR 50 mg and GZR 100 mg. The PK target has been defined by the clinical PK comparability bounds, within which there were no clinically important differences for safety and efficacy; 2) to establish the tolerability, safety, and efficacy of the combination therapy in the pediatric HCV-infected population. All participants will receive EBR/GZR without RBV for 12 weeks.

The trial will enroll participants into three Age Cohorts:

1. Age Cohort 1 (aged 12 years to less than 18 years)
2. Age Cohort 2 (aged 7 years to less than 12 years)
3. Age Cohort 3 (aged 3 years to less than 7 years)

Each Age Cohort starts with a Mini Age Cohort of 7 participants before enrolling additional participants into the Expanded Age Cohort. The enrollment requirements for the Mini and Expanded Age Cohorts are shown in [Table 2](#).

Table 2 Enrollment Requirements for Each Age Cohort

Age Cohort	Age Range	Enrollment Requirements	
		Mini Cohort	Expanded Cohort
1	12 to <18 years	
 • N=7 (to ensure at least 6 participants with evaluable PK) • At least 2 participants aged <14 years 	
 • N=~15 • At least 3 participants aged 12 to <14 years • At least 3 participants aged 16 to <18 years
2	7 to <12 years	
 • N=7 (to ensure at least 6 participants with evaluable PK) • At least 2 participants aged <9 years 	
 • N=~20 • At least 5 participants aged 7 to <12 years • At least 5 participants aged 3 to <7 years 
 ○ At least 2 participants aged <5 years
3	3 to <7 years	
 • N=7 (to ensure at least 6 participants with evaluable PK) • At least 2 participants aged <5 years 	

The enrollment of participants will occur as follows:

1. Mini cohorts of the two oldest Age Cohorts will enroll in the first wave of participants.
 - a. Mini Age Cohort 1
 - b. Mini Age Cohort 2

Enrollment into Mini Age Cohort 2 will follow Mini Age Cohort 1 by 2 to 3 weeks to allow time to review Day 1 PK (AUC) in a minimum of 6 participants of Mini Age Cohort 1 before enrolling Mini Age Cohort 2. The Week 4 intensive PK from the first two Mini Age Cohorts (N=~14), in addition to the Day 1 and Week 8 sparse PK, will be used to update the population PK and PBPK models to select optimal doses for Mini Age Cohort 3 and Expanded Age Cohort 1.

2. Mini Age Cohort 3 and Expanded Age Cohort 1 will enroll in the second wave of participants after optimal doses have been selected based on PK modeling results from the first wave of participants.
 - a. Expanded Age Cohort 1 will enroll following completion of the PK modeling analyses; dosing will use the proposed dose for each component, EBR and GZR, and dose recommendation by weight bands will be used.
 - b. Mini Age Cohort 3: PK modeling and simulation will be used to propose dosing for each component, EBR and GZR. Dose recommendation by weight bands will be used for Mini Age Cohort 3.

Data from the three Mini Age Cohorts and from Expanded Age Cohort 1 will be used to update the population PK and PBPK models in order to propose doses for Expanded Age Cohorts 2 and 3.

3. Expanded Age Cohorts 2 and 3 (Expanded Age Cohort 2/3)

- a. Expanded Age Cohorts 2 and 3 are combined as a single group Age Cohort 2/3. This age cohort will enroll following completion of the updated PK modeling analyses that incorporates PK data from all previous cohorts, including all 21 participants from the three Mini Age Cohorts and all 15 participants from Expanded Age Cohort 1. Dosing of Expanded Age Cohort 2/3 will use the modeling and simulation proposed dose for each component, EBR and GZR.

While age cohorts are used for the purposes of enrollment, dose recommendations by weight bands will be used for Mini Age Cohort 3 and the Expanded Age Cohorts. Weight bands will be determined based on the PK analyses.

Following the conclusion of this study and the Clinical Study Report (CSR) for the study, a final PK model will be developed that includes all PK data from participants aged 3 years up to 18 years, in addition to relevant adult data previously collected in the program. The final model and proposed pediatric dosing regimen will be summarized in a separate report.

PK samples will be collected in all pediatric participants according to the sampling scheme in [Table 9](#). At Day 1 (Mini Age Cohort 1 only) and TW4 (all participants), an overnight stay is recommended to obtain PK samples over a 24-hour period (intensive PK).

In order to reduce PK variability, enrollment in the Mini Age Cohorts will be limited to noncirrhotic participants of non-Asian Race who are not currently taking methadone or strong CYP3A inhibitors. The Mini Age Cohorts will also exclude participants below a weight as described in the inclusion/exclusion criteria; the Expanded Age Cohorts will enroll a broader population as described in the inclusion/exclusion criteria.

Specific procedures to be performed during the trial, as well as their prescribed times and associated visit windows, are outlined in the Trial SoA - Section 2. Details of each procedure are provided in Section 9 – Study Assessments and Procedures.

This trial will use an independent, external Data Monitoring Committee (eDMC) to monitor safety. Periodic safety analyses will be conducted and reviewed by the eDMC at regular intervals as outlined in the eDMC Charter.

The eDMC will make recommendations to the Sponsor to continue, modify, or end the trial according to Section 10 - Statistical Analysis Plan (SAP).

5.1.1 Study Diagram

The trial design is depicted in [Figure 2](#).

[figure not shown]

Figure 2 Trial Design

5.2 Number of Participants

Approximately 56 participants will be allocated as described in Section 10.1.

5.3 Beginning and End of Study Definition

The overall study begins when the first participant (or the participant's legally acceptable representative) signs the informed consent/assent form (ICF). The overall study ends when the last participant completes the last study-related phone-call or visit, withdraws from the study or is lost to follow-up (i.e. the participant is unable to be contacted by the investigator).

5.3.1 Clinical Criteria for Early Study Termination

1. The eDMC recommends termination of the trial and the Executive Oversight Committee (EOC) agrees per Appendix 3 – Committee Structure - Data Monitoring Committee, Appendix 3 – Study and Site Closure, or as stated in the DMC charter.
2. The clinical trial may be terminated early if the extent (incidence and/or severity) of emerging effects/clinical endpoints is such that the risk/benefit ratio to the trial population as a whole is unacceptable.

5.4 Scientific Rationale for Study Design

5.4.1 Rationale for Study Population

Participants in this trial will include noncirrhotic or compensated cirrhotic pediatric participants who are either TN or PR-TE and infected with HCV GT1b/1-other; or with HCV GT1a without a baseline NS5A RAS at position 28, 30, 31, and/or 93; or TN and infected with GT4 and HCV RNA <800,000 IU/mL; and who meet other inclusion/exclusion criteria as described in Section 6. Because PK exposure is independent of GT, the information obtained and doses proposed in this trial can be extrapolated to other GTs for final dosing and administration guidance. The final administration recommendations with regards to duration and need for RBV will be similar to the adult recommendations. Children enrolled in this trial will all be eligible for a 12-week RBV-free regimen, ie, this trial will enroll participants who are HCV GT1b/1-other; HCV GT1a without a baseline NS5A RAS at position 28, 30, 31, and/or 93; or are HCV GT4 with HCV RNA <800,000 IU/mL.

5.4.2 Rationale for Endpoints

5.4.2.1 Efficacy Endpoints

The measurement for efficacy in this trial is the plasma HCV RNA level. Long-term suppression of HCV RNA, typically reported as SVR, has been associated with improved outcomes in subjects with chronic hepatitis C infection as measured by biochemical and histological remission of liver disease. Most available data suggest that SVR following antiviral therapy reduces the risk of progression to cirrhosis and may prevent the development of severe liver complications and improve survival [Alberti, A. 2011].

The evaluation of efficacy in this trial is based on SVR₁₂, the same endpoint used for all investigational and approved DAAs. Since a high degree of concordance has been observed between SVR₁₂ and SVR₂₄ [Martinot-Peignoux, M., et al 2010], SVR₁₂ is used as the primary endpoint for registration of DAAs. For this trial, an evaluation of efficacy based on SVR₂₄ will be an exploratory analysis [Chen, J., et al 2013].

5.4.2.1.1 Measurement of HCV RNA

HCV RNA plasma levels will be measured using the Roche COBAS[®] AmpliPrep/COBAS[®] TaqMan[®] HCV Test, v2.0 on blood samples drawn from each participant at various time points prior to, during, and after dosing, as indicated in the SoA (Section 2).

They are also used to identify participants who meet HCV virologic failure criteria. HCV RNA levels are described as detailed in [Table 3](#).

Table 3 Nomenclature for Describing HCV RNA Levels

Abbreviation	Definition	HCV RNA Level
TND	Target not detected	HCV RNA not detected
TD(u)	Target detected but unquantifiable	HCV RNA <LLOQ
TD(q)	Target detected, quantifiable	HCV RNA ≥LLOQ

Definition of Efficacy Endpoints

Efficacy will be defined at different timepoints during the trial. Specific endpoints are:

- **SVR₁₂**: Participant has HCV RNA <LLOQ (either TD[u] or TND) 12 weeks after the end of all study therapy.
- **SVR₂₄**: Participant has HCV RNA <LLOQ (either TD[u] or TND) 24 weeks after the end of all study therapy.

Definition of Virologic Failure

Lack of efficacy at different timepoints in the trial will be categorized as:

- **Non-response**: Participant has HCV RNA detected at end of treatment without HCV RNA <LLOQ having been achieved while on treatment (note that breakthrough is captured below).
- **Rebound**: Participant has a rebound defined as $>1 \log_{10}$ IU/mL increase in HCV RNA from nadir while on treatment and confirmed from a separate blood draw within 2 weeks.
- **Virologic breakthrough**: Participant has a confirmed HCV RNA \geq LLOQ (TD[q]) after being <LLOQ previously while on treatment. Confirmation is defined as an HCV RNA \geq LLOQ from a separate blood draw repeated within 2 weeks.
- **Relapse**: Participant has a confirmed HCV RNA \geq LLOQ (TD[q]) following end of all study therapy, after becoming undetectable (TND) at end of treatment. Confirmation is defined as an HCV RNA \geq LLOQ from a separate blood draw repeated within 2 weeks.

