Prior/Concomitant Medication Review	X	X	X	X	X	X	X	X	X	X	X	X	X	X	X	Only non-study HCV medications will be queried during Follow-up weeks	
Treatment Allocation	X																
Distribute Study Medication and Meal Diary (SMD) and review instructions		X	X	X	X	X	X										
Review SMD			X	X	X	X	X	X						X			

Trial Period	Screening	Treatment							Follow-up							Unscheduled		Notes
		Day 1	TW 2	TW 4	TW 6	TW 8	TW 10	TW 12	FW 4	FW 8	FW 12	FW 16	FW 20	FW 24	Unshed/ HCV VF Conf Visit	Early Discon Visit		
Visit Number>Title	1	2	3	4	5	6	7	8	9	10	11	12	13	14	15	16	Day 1 procedures to be performed prior to 1 st morning dose unless otherwise specified. FW8, FW16, & FW20 are via phone contact w/the participant or the participant's legally acceptable representative to make sure he/she is doing well and FW24 visit reminder	
Scheduled Hour, Day, Week, etc., and Window:	-45	NA	TW4: -3 to +3 days All other TW: -7 to +7 days							-2 to +2 weeks							NA	Participants should be allocated within a 45 day screening window
Reconcile Study Medication/Assess Compliance with EBR/GZR			X	X	X	X	X	X								X		
Drug Administration																		
Placebo to EBR/GZR (FDC) Administration	X																Placebo is given once prior to allocation to participants in Mini Age Cohort 1 to test whether the participant can swallow the tablet. If it is determined by PK analysis that Expanded Age Cohort 1 will also receive the adult FDC dose, then placebo will be given once prior to allocation to participants in Expanded Age Cohort 1. If the participant cannot swallow the placebo tablet then they cannot be allocated into the trial. Placebo tablets are different in color but identical in size and shape to the active EBR/GZR FDC tablets.	
Dispense EBR/GZR (open label)		X	X	X	X	X	X											
HCV Evaluations																		
HCV Genotype Determination	X																	
Liver imaging	X																For cirrhotic participants only, imaging (eg, ultrasound) is required within 6 months prior to allocation to rule out HCC.	
HCV RNA Level	X			X		X		X	X		X		X	X	X		If a participant is confirmed HCV viral failure during therapy (ie, break through), then the sample collection for HCV RNA is not needed for the early discontinuation visit. Leftover main study plasma from HCV RNA will be stored for FBR if the participant/legally acceptable rep consents to FBR.	

Trial Period	Screening	Treatment							Follow-up							Unscheduled		Notes

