9.11.4 Discontinued Participants Continuing to be Monitored in the Study

Discontinuation during Treatment Period

Participants who discontinue therapy prior to the last scheduled treatment visit should complete an Early Discontinuation visit and then continue into follow-up visits.

During the Early Discontinuation visit, every effort should be made to:

- Perform all procedures and evaluations per the SoA
- Retrieve all study medication(s) from the participant
- Schedule follow-up contact(s) (telephone or site visit) as appropriate
- Collect the following information, at a minimum:
 - Reason the participant discontinued
 - Date of the last dose of study medication
 - Date of the last assessment and/or contact.
 - All AEs.

Discontinuation for Virologic Failure

Participants who discontinue because they have met criteria for virologic failure (Section 5.4.2.1.1 – HCV RNA Measurements and Endpoint Definitions) while on study therapy should complete an Early Discontinuation visit as outlined in the SoA (Section 2), and will be seen for follow-up visits at 4, 12, and 24 weeks following confirmation of virologic failure.

Participants who meet the virologic failure criterion for relapse (HCV RNA \geq LLOQ following the end of all study therapy, after becoming TND at the end of treatment) will be seen for the remainder of their follow-up visits (eg, 4, 12, and 24 weeks) as outlined in the SoA (Section 2).

Participants who have met virologic failure criteria and are identified as having a treatment-emergent RAS, will be offered follow-up in a 3-year long-term follow-up protocol, MK-5172-017, to determine the persistence of RASs and to determine time course of reversion to wild-type.

Discontinuation during Follow-up Period(s)

Participants who discontinue during the follow-up period (eg, FW4 through FW24) for reasons other than virologic failure should complete an Early Discontinuation Visit as outlined in the SoA (Section 2).

At a minimum, the following information should be collected:

- The reason the participant discontinued.
- The date of the last assessment and/or contact. A follow-up contact (telephone or visit) will be arranged as appropriate.
- SAEs (per reporting requirements outlined in Section 9.3 – Adverse Events, Serious Adverse Events and Other Reportable Safety).

10. Statistical Analysis Plan

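### TD(u) at end of treatment followed by confirmed quantifiable HCV RNA in follow-up fits no virologic failure category, because relapse requires TND

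*Combined protocol and SAP*

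**What the plan says.** Table 3 in Section 5.4.2.1.1 separates three results: TND, TD(u) (detected but below LLOQ) and TD(q) (at or above LLOQ). The definitions that follow use different thresholds:

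- SVR12: "Participant has HCV RNA <LLOQ (either TD[u] or TND) 12 weeks after the end of all study therapy". SVR24 is the same at 24 weeks.
- Non-response: RNA detected at end of treatment "without HCV RNA <LLOQ having been achieved while on treatment (note that breakthrough is captured below").
- Rebound: a rise of more than 1 log10 from nadir, on treatment.
- Breakthrough: confirmed TD(q) "after being <LLOQ previously while on treatment".
- Relapse: confirmed TD(q) "following end of all study therapy, after becoming undetectable (TND) at end of treatment".

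Section 9.11.4 restates the relapse condition as "following the end of all study therapy, after becoming TND at the end of treatment". It describes only one other route, for participants who meet failure criteria "while on study therapy should complete an Early Discontinuation visit as outlined in the SoA (Section 2"). The HCV RNA note in the Schedule of Activities uses breakthrough for an on-therapy event: "If a participant is confirmed HCV viral failure during therapy (ie, break through").

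The categories are used in three places. Section 10.6.3 plans summary rates for the four failure types. Section 5.4.2.1.2 commits to RAS assessment when virus exceeds 1000 IU/mL and a failure criterion has been met. Section 4 has the exploratory objective "To evaluate the emergence of NS3 and NS5A RASs in participants with virologic failure".

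**The concern.** Relapse is the only definition here that demands TND as its starting state. Success needs only <LLOQ, and so does the state before breakthrough. TD(u) at end of treatment therefore counts as suppressed for those purposes but not for relapse. The TND condition appears in two sections, so it cannot be set aside as a slip in one of them.

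Two things are at stake. A participant whose virus returns after therapy could be missing from the failure-type summary. The same participant would also not meet the stated trigger for RAS assessment. In a trial of about 56 children with few expected failures, each failure carries weight in those descriptive outputs.

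**Working it through.** **Step 1. Apply each definition to TD(u) at end of treatment, then confirmed TD(q) in follow-up.**

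| Category | Met? | Reason |
|---|---|---|
| Non-response | No | <LLOQ was reached on treatment |
| Rebound | No | Limited to rises on treatment |
| Relapse | No | Not TND at end of treatment |
| Breakthrough, as an on-therapy event | No | The TD(q) arises after therapy |
| Breakthrough, read literally | Yes | The words on treatment attach only to the earlier <LLOQ value |

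**Step 2. Count the patterns.** HCV RNA is measured on treatment at TW4, TW8 and TW12 (Schedule of Activities; Table 16). Three results at three visits give 3 × 3 × 3 = 27 patterns. Remove those with TD(q) after an earlier <LLOQ value, which are on-treatment breakthrough if confirmed. What is left is a run of TD(q) results, possibly empty, followed only by <LLOQ results:

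- no leading TD(q): 2 × 2 × 2 = 8
- one: 2 × 2 = 4
- two: 2
- three: 1

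The total is 15. Of these, 4 + 2 + 1 = 7 end TND, 7 end TD(u) and 1 is TD(q) throughout. Let each be followed by confirmed TD(q) in follow-up:

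| Rule | Relapse | Non-response | Breakthrough | Unclassified |
|---|---|---|---|---|
| Current text, breakthrough on therapy | 7 | 1 | 0 | 7 |
| Current text, breakthrough literal | 7, all also breakthrough | 1 | 14 | 0 |
| Relapse from <LLOQ, breakthrough on therapy | 14 | 1 | 0 | 0 |

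These are counts of possible patterns, not probabilities. They assume that on-treatment TD(q) values are confirmed and that TW12 is observed. Rebound is not modelled, because it needs quantities rather than categories.

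**Step 3. Scale.** The documents do not give the frequency of TD(u) at end of treatment, so an expected number of cases cannot be computed. Two reference points for all non-SVR12:

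- Adult 12-week rows of Table 1: successes 441 + 297 + 54 = 792; participants 450 + 301 + 55 = 806; non-SVR12 = 806 − 792 = 14. Then 14/806 = 1.74%, and 0.0174 × 56 = 0.97.
- Planned response of about 95% (Section 10.9.2): 0.05 × 56 = 2.8.

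**Step 4. Effect of one case on a cohort's relapse rate.** These are Clopper-Pearson 95% limits. For 0/22 the upper limit is 1 − 0.025^(1/22) = 15.4%. The upper limits reproduce Table 14.

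| N | Counted as relapse | Left out |
|---|---|---|
| 22 | 4.5% (0.1 to 22.8) | 0% (0 to 15.4) |
| 15 | 6.7% (0.2 to 31.9) | 0% (0 to 21.8) |
| 12 | 8.3% (0.2 to 38.5) | 0% (0 to 26.5) |

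**The case against.** The strongest reply is that the defect has little practical reach.

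- **Resistance testing is not confined to labelled failures.** Section 9.2.2 has follow-up samples collected to look for emerging resistance, without requiring a failure label. Section 10.6.5.3 describes testing for all participants as well as for failures. Section 10.6 leaves methods for exploratory objectives to the sSAP. This stands: samples are drawn at FW4, FW12 and FW24 whatever the label, and testing is not barred. What is missing is the trigger that makes assessment mandatory under Section 5.4.2.1.2. The long-term follow-up offer also rests on a met failure criterion and, in Section 9.11.4, on a treatment-emergent RAS as well.
- **The supportive SVR12 analysis is probably safe.** A reader might infer that such a participant, on leaving early for an unrelated reason, would be dropped under TRD=F. Section 10.6.3 counts documented virologic failure in follow-up as failure and does not require one of the four labels. Any effect is therefore doubtful.
- **Breakthrough might absorb the case.** The literal wording allows it, but every relapse would then also be breakthrough, which leaves relapse without content of its own. The Schedule of Activities points the other way. The literal reading is unlikely, so it neither answers the gap nor deserves to be pressed as a second major fault.
- **Cases may never occur.** This is true, and it limits the severity. It does not supply the missing category.

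**Conclusion.** The point holds and is minor. With breakthrough read as an on-therapy event, the definitions leave TD(u) at end of treatment followed by confirmed TD(q) without a failure category. The case is then omitted from the relapse rate in Section 10.6.3 and does not meet the stated criterion for required RAS assessment. If one occurs in a cohort of 22, the table reads 0/22 instead of 1/22.

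Three stronger readings are not supported:

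- A reader might infer that SVR12 is biased. The key analysis (FAS, M=F) depends on the result 12 weeks after therapy, not on the failure label. The PK endpoints and the sampling schedule are also untouched.
- A reader might take the Table 1 figure of about 1.0 in 56 as an upper limit. It is not one, because the plan's own 95% assumption gives 2.8. Both figures cover all non-SVR12, and only an unknown part would be TD(u) at end of treatment.
- A reader might take 7 of 15 patterns to mean that nearly half of failures are affected. The patterns carry no probabilities.

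**What to change.** 1. In Sections 5.4.2.1.1 and 9.11.4 together, define relapse as confirmed HCV RNA ≥LLOQ after all study therapy has ended, in a participant whose end-of-treatment result was <LLOQ (TND or TD[u]).
2. In Section 5.4.2.1.1, state that breakthrough is HCV RNA ≥LLOQ first observed on treatment, after an earlier on-treatment value <LLOQ, and confirmed by a repeat draw within 2 weeks.

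This closes the TD(u) gap and removes the overlap between breakthrough and relapse. It does not settle every case. If TW12 is TD(q) after an earlier <LLOQ value but is never confirmed, a later confirmed TD(q) still has no category. A missing TW12 value is also open. If the intermittent-missing rule in Section 10.6.3 were applied, TND at TW8 and TD(q) at FW4 would impute TD(q) at end of treatment, and the revised relapse definition would not be met. The sponsor could state a rule for both cases in the sSAP.

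The cost is one phrase for relapse in two sections and one phrase for breakthrough. There are no added visits or blood draws; any extra work is RAS testing of plasma already scheduled. The treatment-discontinuation rule in Section 8.1 is unaffected, because the values at issue arise after therapy has ended.
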